5.8 EVALUATIONS AT END OF TREATMENT

The *end-of-treatment visit* will be scheduled within 30 days (\pm 7 days) after the last PM01183 infusion, unless the patient starts a subsequent antitumor therapy, in which case the end-of-treatment visit should be performed immediately before the start of the new therapy (ideally the day before or the same day).

Patients, regardless of the reason for ending the treatment, will have to undergo at the end of treatment the following assessments:

- Complete physical examination.
- ECOG PS.
- Vital signs.
- Concomitant therapies.
- Laboratory tests (coagulation panel, hematology and biochemistry A and B).
- Pregnancy test, ECG or LVEF assessment (if clinically indicated).
- Radiological tumor assessment (the evaluation should be repeated at EOT visit, if not previously done, and if the reason for treatment discontinuation is other than PD).
- Adverse events.

These evaluations will only have to be repeated for those parameters for which no measurement is available within 10 days before the EOT visit, or for those parameters with values that were out of range in the last assessment (grade \geq 2 according to the NCI-CTCAE v.4).

Adverse events must be reported for 30 days after the last study treatment administration. All serious adverse events (SAEs) occurring within 30 days of the last study treatment administration or until the start of a new antitumor therapy, whichever occurs first, will be reported. Beyond this period of time, only those suspected to be treatment-related SAEs will be reported (Section [7.7.2](#)).

The Sponsor will evaluate all safety information that is spontaneously reported by an Investigator beyond the time frame specified in the protocol.

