7.7 ADVERSE EVENTS REPORTING PROCEDURES

7.7.1 Reporting Adverse Events

The Sponsor will collect AEs until 30 days after administration of the last dose of the study drug(s)/IMP(s) or until the start of a new antitumor therapy, whichever occurs first. All AEs suspected to be related to the study drug/IMP must be followed-up after the time of therapy discontinuation until the event or its sequelae resolve or stabilize at an acceptable level to the Investigator and the Sponsor.

All AEs, including misuse, overdose and abuse, must be recorded in English using medical terminology in the source document and the CRF. Whenever possible, the Investigator will record the main diagnosis instead of the signs and symptoms normally included in the diagnoses.

Investigators must assess severity (grade) of the event following the NCI-CTCAE v.4 and assign a relationship to each study drug(s)/IMP(s); and pursue and obtain information adequate both to determine the outcome and to assess whether it meets the

criteria for classification as a SAE requiring immediate notification to Pharma Mar or its designated representative. The Investigator must provide any relevant information as requested by the Sponsor in addition to that on the CRF.

Abnormal laboratory tests occurring during the study should only be recorded in the AE section of the CRF if the disorder:

- Is associated with clinically significant symptoms, and/or
- Leads to a change in study dosing or discontinuation from the study, significant additional concomitant drug treatment or other therapy, and/or
- Leads to any of the outcomes included in the definition of a SAE.

Otherwise laboratory results should be reported in the corresponding section of the CRF (i.e., biochemistry, hematology).

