7.1 Toxicity and Adverse Events

All the adverse events will be coded using the Medical Dictionary for Regulatory Activities (MedDRA).

The toxicity evaluation will be coded with the National Cancer Institute Common Terminology Criteria for Adverse Events (NCI-CTCAE) v4.

Treatment-emergent adverse events (TEAE) are defined as any adverse events aggravated in severity from baseline or having their onset between the first dose of the study drug and 30 days after the last treatment dose, death or date of further therapy (whichever comes first). Adverse Events Related to Study Drug or with Unknown relationship occurring more than 30 days after the last dose will also be taken into account as TEAEs.

Summary of overall AEs will be done by System Organ Class (SOC) and Preferred Term (PT), by severity (worst toxicity grade), by relationship to the study drug and by AE outcome. Tables will be

organized by category of events using SOC (i.e. alphabetical order) and PT in descending frequencies (i.e., from higher to lower).

A frequency table or listing will be made for the AEs leading to cycle delay, dose reduction or withdrawal of study medication. Adverse events with outcome of death will also be presented by relationship to the study drugs.

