12.2.2 Display of Treatment Emergent Adverse Events

Table 12.2.2.1 Summary of treatment emergent adverse events per patient.

Category**	N	%
Patients with at least one TEAE regardless of relationship		
Any treatment-related** AE		
Any grade ≥3 TEAE		
Any treatment-related grade ≥3 AE		
Any Treatment emergent SAE in DB		
Any treatment-related SAE		
Any grade ≥3 Treatment emergent SAE		
Any treatment-related grade ≥3 SAE		
TEAEs leading to death		
Treatment-related AE leading to death		
TEAEs leading to dose delay***		
TEAEs leading to dose reduction***		
TEAEs leading to treatment discontinuation		
Treatment-related AEs leading to treatment discontinuation		

Note: Also for s1 and s2; (*) Percentage based on number of treated patients; (**) Treatment related adverse event is every event whose relationship is 'Yes' or 'Unknown'. (***) TEAEs leading to dose delay and reduction according to the AE form, with no delay or reduction because the patient discontinues treatment and there is no additional cycle administered are not counted here.

Table 12.2.2.2 Treatment-related adverse events. Worst grade by patient.

Table 12.2.2.3 Treatment-related adverse events. Worst grade by cycle.

Table 12.2.2.4 Treatment emergent adverse events regardless of relationship. Worst grade by patient.

Table 12.2.2.5 Treatment emergent adverse events regardless of relationship. Worst grade by cycle.

Tables 12.2.2.2 to 12.2.2.5 will have the following pattern, but depending on the number and severity of the adverse events observed, the NCI-CTCAE v4 grades may be grouped as ≥1 and ≥3 categories.

SOC	Preferred term	Grade 1		...	Grade 4		Grade ≥1		Grade ≥3
		N	%		N	%	N	%	
Blood and lymphatic system disorders	Anemia NOS			...					
	...								
	...								
Cardiac disorders	Arrhythmia NOS								
	...								

Note: Tables 12.2.2.2 and 12.2.2.4 also for s1 and s2.

Listing 12.2.2.6 Treatment-related grade ≥3 adverse events. Worst grade per patient.

Listing 12.2.2.7 Treatment-related grade ≥3 adverse events. Worst grade by cycle.

Listing 12.2.2.8 Grade ≥3 treatment emergent adverse events regardless of relationship. Worst grade per patient.

Listing 12.2.2.9 Grade ≥3 treatment emergent adverse events regardless of relationship. Worst grade by cycle.

Listings 12.2.2.6 to 12.2.2.9 will have the following pattern:

Patient id.	CTFI**	Cycle*	SOC name	Preferred term	Grade

(*) NA in the per patient summaries; (**) CTFI only for SCLC patients (RR, R, S, VS).

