12.3.2 Deaths

Table 12.3.2.1 Cause of death.

Reason*	N	%
Malignant disease		
Study drug-related TEAE		
Non-study drug-related TEAE		
Other		
Total		

Note: Also for s1 and s2; (*) Denominator=Number of patients who died.

Listing 12.3.2.2 Deaths.

Patient id.	CTFI***	Death date	Cause	No. of cycles administered	Last infusion date	Time on treatment*	Time from Last dose**	Comments	Autopsy

(*) Time on treatment: defined as date of last infusion plus 30 days, or date of death or subsequent therapy (whichever comes first) minus date of first infusion. (**) Time from last dose defined as date of death minus date of last infusion. (***) Only for SCLC cohort (RR, R, S, VS).

Listing 12.3.2.3 Adverse events with outcome of death.

Patient id.	Cycle	Preferred term code	Adverse event reported (verbatim)	Grade	Relationship	Onset date	Date of death	Action

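### Minor: the TEAE rule in SAP 7.1 leaves out related events that start after further therapy and by day 30, yet counts the same events from day 31

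*SAP*

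**What the plan says.** SAP 7.1 gives three routes to TEAE status.

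- An event that worsens in severity from baseline qualifies.
- A new event qualifies if its onset lies between the first dose and "30 days after the last treatment dose, death or date of further therapy (whichever comes first".
- An event related to study drug, or of unknown relationship, also qualifies when "occurring more than 30 days after the last dose will also be taken into account as TEAEs".

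SAP 8.4 foresees patients starting new antitumor therapy within 30 days of the last dose and takes that start as the date of treatment discontinuation.

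On data collection, Protocol 7.7.1 ends general AE collection 30 days after administration "of the last dose of the study drug(s)/IMP(s) or until the start of a new antitumor therapy, whichever occurs first". Protocol 5.8 sets the same limit for SAEs and then adds: "Beyond this period of time, only those suspected to be treatment-related SAEs will be reported". Protocol 7.7.2 says the same of SAE collection.

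The flag is used in SAP 12.2.2, in the row "Any Treatment emergent SAE in DB" of Table 12.2.2.1 and in "Table 12.2.2.4 Treatment emergent adverse events regardless of relationship. Worst grade by patient", among others. SAP 12.3.2 has a cause-of-death row labelled "Study drug-related TEAE".

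**The concern.** The second and third routes do not meet. The window is cut short by further therapy, but the exception for related events is counted from the last dose, not from the point where the window closed. Between the two lies a stretch of days on which a new-onset related event has no route to TEAE status. The result is perverse: of two identical related events, the one nearer the last dose is excluded and the later one is counted.

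The events concerned are not hypothetical blanks in the database. The protocol's own exception for related SAEs starts exactly where its collection window ends, so related SAEs after early further therapy are collected. The SAP then leaves them unflagged.

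What is at stake is the accuracy and internal consistency of the TEAE tables. There is also a programming ambiguity. The title of Table 12.2.2.1 limits it to treatment-emergent events, but its footnote reads "Treatment related adverse event is every event whose relationship is" Yes or Unknown, with no onset condition. Two programmers could defensibly produce different counts for the related rows.

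**Working it through.** This is a check of a definition, so the plan has no stated figure to reproduce.

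**Notation.** Count days from the last dose. Let T be the day further therapy starts and d the onset day of a new event that is related or of unknown relationship.

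**Rule as written (SAP 7.1).**
- Window: d ≤ min(30, T). Death also closes the window, but no new onset follows death.
- Exception: d > 30.
- Covered by neither: T < d ≤ 30, which is 30 − min(30, T) days.

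**Results.** The values of T are illustrative; the documents give none.

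| T | Days left out | Length (30 − min(30, T)) | Day 31 a TEAE? |
|---|---|---|---|
| 10 | 11–30 | 30 − 10 = 20 | yes |
| 15 | 16–30 | 30 − 15 = 15 | yes |
| 20 | 21–30 | 30 − 20 = 10 | yes |
| 21 | 22–30 | 30 − 21 = 9 | yes |
| 28 | 29–30 | 30 − 28 = 2 | yes |
| 29 | 30 | 30 − 29 = 1 | yes |
| 30 or later, or none | none | 0 | yes |

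**Can another reading close the gap?**
- Applying the 30 days to all three closing events would give a window of 30 days after death, which has no meaning. SAP 8.4 also treats the start of new therapy itself as the cut-off.
- Calling any new event a worsening from baseline would make the onset window redundant.
- The TEAE rules in SAP 8.9 deal only with incomplete dates.

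**Effect on Table 12.2.2.1.** Take one patient whose only SAE is related, with T = 21 (assumed).

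| Onset and rule | All-cause treatment-emergent SAE row | Related SAE row, footnote reading | Related SAE row, title reading |
|---|---|---|---|
| d = 25, as written | 0 | 1 | 0 |
| d = 31, as written | 1 | 1 | 1 |
| d = 25, exception starting at end of window | 1 | 1 | 1 |

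On the footnote reading, the first line shows a related event that is missing from the all-cause total it should belong to. On the title reading, the related SAE is missing from both rows.

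**Other displays.** The same event drops out of the grade ≥3 treatment-emergent SAE row if it is that severe, out of the row for TEAEs leading to death if it is fatal, and out of Tables 12.2.2.4 and 12.2.2.5. Read literally, a fatal one also drops out of the related row of Table 12.3.2.1.

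**The case against.** The other side accepts that the gap exists on the text and disputes how much it matters.

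- **Intent and the footnote.** The exception is plainly meant to keep related events after the window closes, and a footnote that defines a row should outrank a table title. On that view no related row loses anything. This is the more natural reading of the related rows, but it does not repair the all-cause rows, where the mismatch remains.
- **Other displays.** The SAE tables and listing in SAP 12.3.1, Listing 12.3.2.3 of fatal AEs, and Listings 14.1.21 and 16.2.7 are not limited to TEAEs. This stands: the events are not hidden.
- **Table 12.3.2.1.** Cause of death is a field on the death report form (Listing 14.1.27), and nothing says the row is derived from the TEAE flag. This is fair; the effect there follows only from a literal reading of the label.
- **Frequency.** A gap event needs further therapy before day 30, a new onset by day 30, and attribution to study drug (or unknown relationship) despite the new agent. The documents give no rate for any of these. This stands.
- **Match with the protocol.** Protocol 7.7.2 keeps only related SAEs, whereas a corrected SAP sentence would cover all related AEs and those of unknown relationship. That wider scope is already in the SAP's sentence; the match is in where the exception starts.
- **Collection.** Protocol 5.8 also asks for AEs to be reported for 30 days with no cut-off at new therapy, in tension with Protocol 7.7.1. If 5.8 governs, non-serious related events fall in the gap too, which widens it.

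**Conclusion.** The concern holds, as a minor one. As written, SAP 7.1 denies TEAE status to a new-onset related or unknown-relationship event that starts after further therapy and on or before day 30, and grants it to the same event on day 31. The gap lasts 30 − min(30, T) days per patient and exists only when further therapy starts before day 30.

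The conclusion rests on the plain reading that further therapy truncates the window, which SAP 8.4 supports. If Protocol 7.7.1 governs collection, the events at risk are mainly related SAEs. The number of patients is not given and is probably small. The damage is confined to descriptive TEAE counts and their consistency: no efficacy analysis uses the flag, and the stopping rules count treatment-related deaths rather than TEAEs.

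**What to change.** Reword the second sentence of the TEAE definition in SAP 7.1 along these lines: *AEs related to study drug, or of unknown relationship, with onset after the end of this window (30 days after the last dose, or the start of further therapy if earlier) are also TEAEs.*

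The exception then begins where the window closes, as it does for SAEs in Protocol 7.7.2. Every related or unknown-relationship AE with onset after the first dose becomes a TEAE, so the title and footnote readings of Table 12.2.2.1 give the same related counts and the footnote can stay.

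The cost is one sentence and one line of derivation code, with no new data. Counts in the rows labelled treatment-emergent may rise slightly.

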7.2 Clinical Laboratory Evaluation

Laboratory results will be classified according to the NCI-CTCAE v4.

The following hematological values (worst grade per patient and per cycle during treatment) will be displayed: white blood cells count (WBC), neutrophils count, lymphocytes count, platelets count and hemoglobin.

Overall cross tabulation will be presented for the worst grade during treatment *versus* the baseline severity grading of leukopenia, neutropenia, lymphopenia, thrombocytopenia and anemia.

If a grade ≥ 3 neutropenia or thrombocytopenia occurs during a cycle of treatment, the first day it reaches grade 3 or 4 (counting from the start of the cycle) and the duration of the abnormality (i.e., until recovery to grade ≤ 2) will be tabulated.

Similarly, the following biochemical values (worst grade per patient and per cycle during treatment) will be displayed: alanine aminotransferase (ALT), aspartate aminotransferase (AST), total bilirubin, alkaline phosphatase (AP), creatine phosphokinase (CPK), creatinine, gamma-glutamyltransferase (GGT), calcium (corrected by albumin levels), potassium, sodium, magnesium, glucose and albumin.

If a grade ≥ 3 AST or ALT increase occurs during a cycle of treatment, both the day it peaked (counting from the start of the cycle) and the duration of the abnormality (i.e., until recovery to grade ≤ 2) will be tabulated.

Overall cross tabulation will be presented for the worst grade during treatment *versus* the baseline severity grading of biochemical abnormalities.

7.3 Vital Signs, Physical Examination, Left Ventricular Ejection Fraction and Electrocardiogram Findings

Tabulation will be made summarizing the performance status, body weight, left ventricular ejection fraction (LVEF) and electrocardiogram (ECG) abnormalities at baseline and during the treatment, if appropriate, for each cohort and patient.

7.4 Deaths and Other Serious Adverse Events

Deaths and other serious adverse events (SAEs) will be tabulated.

8 OTHER ANALYSES

Continuous variables will be tabulated and presented with summary statistics (i.e., mean, standard deviation, median and range).

Categorical variables will be summarized in frequency tables by means of counts and percentages. Percentages in the summary tables will be rounded and may therefore not always add up to exactly 100%.

8.1 Patient Disposition and Treatment/Study Discontinuation

The number of patients included in the study, the number of patients treated and the number of patients evaluable for the main endpoint will be shown. Also, accrual by center and country and the main dates of the study will be displayed. Reasons for treatment discontinuation and for study discontinuation will be tabulated.

8.2 Protocol Deviations

Analysis of inclusion/exclusion criteria deviations, retreatment restrictions, concomitant medication and clinically relevant discontinuations, among others, will be done as described in Appendix I.

8.3 Baseline and Demographic Data

Baseline data such as demographics, cancer history, prior therapy, prior relevant history, signs and symptoms, ECG, LVEF, physical examination, vital signs, laboratory values and concomitant medication, coded according to the World Health Organization (WHO) Anatomical Therapeutic Chemical (ATC) classification system, will be described following standard tables detailed in Appendix I.

Age, baseline weight, height, and body surface area (BSA) will be summarized descriptively.

Baseline weight and height will be recorded on the case report form (CRF).

Baseline BSA will be calculated using the Dubois & Dubois formula.

Age categories and race will be summarized with frequency counts.

Baseline Eastern Cooperative Oncology Group (ECOG) performance status (PS) will be summarized with frequency counts.

For the cancer history: time from initial diagnosis, time from metastatic disease and time from last progression before the study entry will be recorded. These time calculations will be shown in months and summarized descriptively. Histology and characteristics of the disease at study entry will be tabulated.

Previous relevant medical history (other than cancer) will be listed.

A frequency tabulation of the number of patients with and the different types of previous surgery, radiotherapy, or therapy (number of lines) will be given.

Adverse events at baseline will be displayed by tabulation of frequencies according to NCI-CTCAE v4 toxicity grades. They will also be listed.

In case of pre-treatment characteristics with multiple measurements per patient before the start of treatment (e.g. laboratory assessments, vital signs) the baseline measurement will be considered the last valid value prior to or on the first day of treatment.

8.4 Treatment Administration

Total cumulative dose, dose intensity and relative dose intensity, time on treatment, cycle delays and dose reductions will be described following standard tables detailed in Appendix I.

Total cumulative dose, expressed in mg, will be the sum of all the study drug doses from the first cycle until the last cycle, including the dose received in the last cycle.

Patients will be considered to be on-treatment for the duration of their treatment and for 30 days after the last treatment dose. If the patient starts any new antitumor therapy outside this clinical trial or dies within 30 days of the last treatment dose, the date of administration of this new therapy or the date of death will be considered the date of treatment discontinuation.

However, as a convention, the duration of the last cycle will be considered to be 21 days (instead of 30 days) for dose intensity calculation purposes.

Intended dose intensity is the planned dose per cycle divided by the planned number of weeks per cycle.

Absolute dose intensity is the actual cumulative dose divided by the number of weeks of treatment. Relative dose intensity (%) is the ratio of absolute dose intensity divided by the intended dose intensity.

The CRF item «Infusion delayed: yes/no» will be used to calculate the delayed cycles. For those cycles considered as delayed by the Investigator, the delay will be calculated as follows:

Delay: Date of actual drug administration – Date of previous drug administration – 21.

The infusion of the first cycle will be excluded from all calculations regarding cycle delays and modifications.

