6.3 STARTING DOSES AND SCHEDULE

Starting dose will be 3.2 mg/m². Dose will be capped at BSA of 2.0 m² (i.e., dose will not exceed 6.4 mg).

Patients will receive PM01183 i.v. as a one-hour infusion on Day 1 every three weeks (q3wk) (three weeks = one treatment cycle).

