12.1 Extent of Exposure

12.1.1 Treatment Administration

Table 12.1.1.1 Number of cycles administered and dose intensity.

No. of cycles administered per patient	N	%
1		
2		
3		
...		
Mean, Standard Deviation, Median (Range)		
Time on treatment* (weeks)		
Median		
Range		
Mean		
Standard Deviation		
PM01183 cumulative dose (mg)		
Median		
Range		
Mean		
Standard Deviation		
PM01183 dose intensity (mg/m ² /wk)		
Median		
Range		
Mean		
Standard Deviation		
PM01183 relative dose intensity (%)		
Median		
Range		
Mean		
Standard Deviation		

Note: Also for s1 and s2; (*) Time on treatment: defined as date of last infusion plus 30 days, or date of death or subsequent therapy (whichever comes first) minus date of first infusion.

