Patient id.	Drug	First Intended dose (mg/m2)	Cycles received	Start date (First cycle)	Start date (Last cycle)	Total dose (mg/m2)	Dose intensity per week (mg/m2/wk)	Relative Dose intensity (%)	Delays*	Reductions*

(*) Delays/reductions will be nested for each patient (cycle and reasons of delay/reduction). e.g: C1 hematological toxicity/C3 non drug related.

Listing 16.2.6 Individual Efficacy Response Data.

Patient id.	Best Response by IA	Best Response by IRC*	PFS by IA (months)	PFS by IRC* (months)	DOR by IA (months)	DOR by IRC* (months)	OS (months)

(*) Only for SCLC

Listing 16.2.7 Adverse Event Listing.

Patient id.	Literal	Preferred Term	Grade Coded Value	SAE	Onset date	Resolved date	Relationship	Action taken	Serious criteria

Listing 16.2.8 Listing of Individual Laboratory Measurements by Patient.

				Hemoglobin (g/dL)	WBC (10*9/L)	Neutrophils (10*9/L)	Lymphocytes (10*9/L)	...*
Patient id.	Cycle	Examination date	Laboratory	Std.value	Std.value	Std.value	Std.value	Std.value

(*) Monocytes (x10*9/L), Direct Bilirubin (mg/dl), Total Bilirubin (mg/dl), AST IU/L, ALT (IU/L), AP (IU/L), GGT (IU/L), Glucose (mmol/L), Creatinine (mg/dl), CrCl (mL/min), NA (mmol/L), CL (mmol/L), K (mmol/L), LDH (IU/L), CPK (IU/L), Total Proteins (g/dl), Albumin (g/dl), CA (mmol/L), Mg (mg/dl), INR (ratio), PT (sec/ratio), PTT (sec/ratio), AFP (ng/m), hCG (IU/L), AAGP (mg/dl).

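### SAP 8.4 derives dose intensity in mg/wk but its outputs report mg/m²/wk with no BSA step, and it does not say whether the planned dose is taken after the 6.4 mg cap

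*SAP*

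**What the plan says.** SAP 8.4 (Treatment Administration) gives the definitions in sequence:

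- Cumulative dose: "Total cumulative dose, expressed in mg, will be the sum of all the study drug doses from the first cycle until the last cycle".
- Intended dose intensity: "Intended dose intensity is the planned dose per cycle divided by the planned number of weeks per cycle". No unit is given and the cap is not mentioned.
- Absolute dose intensity: "Absolute dose intensity is the actual cumulative dose divided by the number of weeks of treatment".
- Relative dose intensity: "Relative dose intensity (%) is the ratio of absolute dose intensity divided by the intended dose intensity".
- Last cycle: "the duration of the last cycle will be considered to be 21 days (instead of 30 days) for dose intensity calculation purposes".

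The outputs use other units. Table 12.1.1.1 shows cumulative dose in mg but dose intensity in mg/m²/wk. Listing 16.2.5 heads its total-dose column "Total dose (mg/m2", gives the first intended dose in mg/m², and gives dose intensity in mg/m²/wk. Listing 12.3.1.1 (SAEs) also carries intended dose in mg/m².

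Protocol 6.3 sets a starting dose of 3.2 mg/m² on Day 1 of a three-week cycle and adds: "Dose will be capped at BSA of 2.0 m² (i.e., dose will not exceed 6.4 mg". The dose-level table in Protocol 6.6 attaches the same cap to the 3.2 mg/m² row as a footnote. Under Protocol 5.7 (Table 4), and note 1 to the schedule of assessments, the dose is adjusted for BSA only when BSA has changed by 10% or more.

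**The concern.** A programmer following SAP 8.4 literally obtains mg/wk and has to fill a table cell labelled mg/m²/wk. The missing step is a division by BSA, and the SAP does not say which BSA to use: baseline, the one measured at that cycle, or the one from which the dose was calculated. These can differ, because the dose is left alone for BSA changes under 10%. Two competent programmers could report different values for the same patient.

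The second gap is in the denominator. If the planned dose is taken before the cap, relative dose intensity falls below 100% for large patients who lost no dose to toxicity, delay or non-compliance. A prescribed limit is then mixed with real loss of dose. Table 12.1.1.1 is to be produced by cohort, and also for the SCLC resistant and sensitive groups, so the number will be read as a statement of how well the planned dose was delivered.

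**Working it through.** **Inputs.** Starting dose 3.2 mg/m², cap 6.4 mg and cycle length 3 weeks (Protocol 6.3); definitions from SAP 8.4; reported units from SAP Table 12.1.1.1 and Listing 16.2.5. The documents give no BSA distribution, so the BSA values below are illustrative assumptions.

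**The plan's own figure.** Cap: 3.2 × 2.0 = 6.4 mg, which reproduces. The plan states no dose-intensity value to reproduce.

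**Step 1: units.** For a patient with no delay or reduction over n cycles, cumulative dose is n × min(3.2 × BSA, 6.4) mg over 3n weeks, so n cancels.

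- SAP 8.4 formula: min(3.2 × BSA, 6.4)/3, in mg/wk.
- Quantity the outputs label: the same divided by BSA, in mg/m²/wk.

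**Step 2: denominator.** An uncapped planned dose gives 3.2/3 = 1.067 mg/m²/wk. A capped planned dose gives min(3.2 × BSA, 6.4)/BSA/3. With numerator and denominator both per m², relative dose intensity (RDI) under full compliance is:

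| BSA (m²) | Dose per cycle (mg) | SAP 8.4 formula (mg/wk) | Per m² (mg/m²/wk) | RDI, uncapped planned dose | RDI, capped planned dose |
|---|---|---|---|---|---|
| 1.6 | 5.12 | 1.707 | 1.067 | 100% | 100% |
| 1.8 | 5.76 | 1.920 | 1.067 | 100% | 100% |
| 2.0 | 6.40 | 2.133 | 1.067 | 100% | 100% |
| 2.1 | 6.40 | 2.133 | 1.016 | 95.2% | 100% |
| 2.2 | 6.40 | 2.133 | 0.970 | 90.9% | 100% |
| 2.5 | 6.40 | 2.133 | 0.853 | 80.0% | 100% |

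Above 2.0 m² the uncapped column is (6.4/BSA)/3.2 = 2.0/BSA. For scale, a patient held at dose level -1 throughout would show 2.6/3.2 = 81%.

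**Step 3: which BSA.** Take a patient dosed at BSA 1.80 m² (3.2 × 1.80 = 5.76 mg) whose BSA falls to 1.65 m², a change of 0.15/1.80 = 8.3%. The dose stays at 5.76 mg.

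- Divided by the re-measured BSA: 5.76/1.65 = 3.49 mg/m², or 109% of 3.2.
- Divided by the BSA used for dosing: 5.76/1.80 = 3.20 mg/m², or 100%.

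In the other direction, a rise from 1.70 to 1.85 m² (8.8%) leaves 3.2 × 1.70 = 5.44 mg. Then 5.44/1.85 = 2.94 mg/m², or 92%, against 5.44/1.70 = 3.20 mg/m², or 100%. Only the dosing BSA returns 100% for a patient treated exactly to protocol.

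**The case against.** The case for leaving this alone has several parts.

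- **The cap may already be included.** SAP 8.4 refers only to a planned dose, and the protocol states the cap in the sentence after the starting dose. On that reading every compliant patient reaches 100%. This stands: the text does not show that the cap is ignored. The mg/m² intended-dose columns make the uncapped reading plausible, no more.
- **Relative dose intensity need not be in the wrong units.** If the planned dose is in mg, the ratio is mg/wk over mg/wk and is correct. This also stands. A reader might pair the mg numerator of SAP 8.4 with the mg/m² intended dose of Listing 16.2.5 and infer values of 160% at 1.6 m², 180% at 1.8 and 200% from 2.0 m² upward. SAP 8.4 gives no unit for the planned dose, so the documents do not support that as the defined calculation.
- **SAP 8.15 defers conventions to a separate document.** That covers only what is not in the SAP. These quantities are in it, with a formula that does not give the reported unit, so the deferral does not cure the conflict.
- **The practical effect is small.** Delays and reductions are tabulated separately with their reasons, and Listing 16.2.5 prints each patient's reductions beside relative dose intensity. A capped patient is therefore unlikely to be mistaken for a reduced one in the listing. This stands for individual patients. The summary rows of Table 12.1.1.1 carry no such cue.

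**Conclusion.** The unit conflict is established from the text alone: the SAP 8.4 formula gives mg/wk, two outputs report mg/m²/wk, total dose is in mg in two places and mg/m² in a third, and no BSA step is stated. The discrepancy in absolute dose intensity is a factor of BSA.

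The cap is an unstated choice, not a demonstrated error. The shortfall of 2.0/BSA rests on two assumptions: that numerator and denominator are on the same scale, and that the planned dose is an uncapped 3.2 mg/m². It applies only above 2.0 m². Without a BSA distribution, its effect on any cohort or on comparisons between tumor types cannot be sized.

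A reader might combine the two gaps and infer that relative dose intensity is both inflated by mixed units and below 100% for capped patients. Those are alternative readings. The mixed-unit ratio gives 200% for a compliant capped patient; values below 100% arise only once the units agree.

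This is a descriptive exposure summary. It has no bearing on ORR or on any stopping or expansion rule. It is worth correcting because it changes a reported figure and costs little.

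**What to change.** Amend SAP 8.4 as follows:

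1. Keep total cumulative dose in mg. Add cumulative dose in mg/m², as the sum over cycles of the mg given divided by the BSA on which that dose was calculated, not the BSA re-measured at that cycle.
2. Define absolute dose intensity as cumulative mg/m² divided by weeks of treatment, with the existing 21-day convention for the last cycle.
3. Define intended dose intensity from the protocol-prescribed starting dose after the existing cap: min(3.2 × dosing BSA, 6.4)/dosing BSA/3. Where the dosing BSA is revised during treatment, average this over the cycles given. Full compliance then gives 100% at every BSA.
4. Use the same units and labels in Table 12.1.1.1 and Listing 16.2.5.

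The cost is a few sentences, one added derived variable and revised column labels. BSA is recorded by visit (Listing 14.1.14), and intended and total dose by infusion (Listing 14.1.20), so nothing new is collected. The dose, the cap and the 10% adjustment rule are taken as they stand.
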